#### *Eligibility Checklist*

The eligibility checklist must be completed by a protocol nurse or clinical research associate and signed by an authorized investigator prior to registering the subject. See Section 4.3 for the registration procedure.

## Protocol Deviations

---

### 14.1.4 Deviation Policy

---

This protocol will be conducted in accordance with COH's "Clinical Research Protocol Deviation Policy" located at <http://www.coh.org/dsmc/Documents/Institutional%20Deviation%20Policy.pdf>.

Deviations from the written protocol that could increase patient risk or alter protocol integrity require prior IRB approval of a single subject exception (SSE) request. In addition, if contractually obligated, the sponsor must also approve the deviation. IRB pre-approved SSE protocol modifications are considered an amendment to the protocol and not a deviation. The submission of a deviation report is not required.

Brief interruptions and delays may occasionally be required due to travel delays, airport closure, inclement weather, family responsibilities, security alerts, government holidays, etc. This can also extend to complications of disease or unrelated medical illnesses not related to disease progression. The PI has the discretion to deviate from the protocol when necessary so long as such deviation does not threaten patient safety or protocol scientific integrity. Examples include, but are not limited to: a) dose adjustments based on excessive patient weight; b) alteration in treatment schedule due to non-availability of the research participant for treatment; c) laboratory test results which are slightly outside the protocol requirements but at levels that do not affect participant safety. These instances are considered to be deviations from the protocol. A deviation report will be submitted to the DSMC/IRB within five days.

### 14.1.5 Reporting of Deviations

---

All deviations will be reported to the COH DSMC within five days. The DSMC will forward to report to the IRB following review.

### 14.1.6 Resolving Disputes

---

The COH Investigational Drug Service (IDS) cannot release a research agent that would cause a protocol deviation without approval by the PI. Whenever the protocol is ambiguous on a key point, the IDS should rely on the PI to clarify the issue.

In situations where there is misperception or dispute regarding a protocol deviation among the persons involved in implementing the protocol, it is the responsibility of the PI to resolve the dispute and the PI may consult with the DSMC chair (or designee) to arrive at resolution.

## 15 STATISTICAL CONSIDERATIONS

---

### Sample Size

---

The anticipated sample size is 29patients: minimum=6; maximum= 53(allowing for 42 patients for dose escalation through 5 possible dose levels of NSCs and 3 dose schedules of irinotecan, estimating ~3 patients to replace unevaluable/ineligible patients and an additional 8 patients for the expansion cohort).A sample size of 6 at the MTD/MFD will allow us to i) achieve a maximum margin of error for a 95% confidence interval for the DLT rate of 0.38 and ii) detect a 0.25 toxicity rate in approximately 82% of trials. The additional 8 patients in the expansion cohort, for a total of 14 patients treated at the MTD/MFD, will allow us to i) achieve a maximum margin of error for a 95% confidence interval for the DLT rate of 0.27 and ii) detect a 0.15toxicity rate in approximately 90% of trials.

An important purpose of the expansion cohort is to obtain information about the biologic activity of the hCE1m6-NSCs using intracerebral microdialysis. Sample size calculations based on preclinical results for the AUC from 0 to 20 hours (nMxhr) for SN38in rats (the combination therapy group mean= 7, sd=4.4; irinotecan alone mean=1.8, sd=1.2) implementing a natural log scale (mean difference 1.36 and sd=0.66) indicate 4 participants per group could provided 80% power todetermine if the addition of NSCs to treatment with irinotecan increases intracerebral concentrations of SN-38, using a one-sided two-sample t test with a 0.05 level of significance. As we expect our patient data to be more variable than the preclinical rat data we consider these results to be exploratory.

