**Study Design:**

This phase I clinical trial will define the recommended phase II dosing (RP2D) based on dose-limiting toxicities (DLTs) and the full toxicity profile of the combination of hCE1m6-NSCs and irinotecan using a standard "3 + 3" dose escalation schema in patients with recurrent highgrade gliomas who are undergoing a debulking craniotomy or stereotactic brain biopsy. Except for dose levels 1 and -1, where only 1 dose of NSCs will be given (these patients can continue to receive treatment with irinotecan every 2 weeks), NSCs will be administered intracranially on days 1 and 15, and irinotecan will be given intravenously 2 days later, on days 3 and 17 of a 28 day cycle. With subsequent cohorts of patients, the NSC dose will be increased as tolerated, but the dose of irinotecan will remain the same unless DLTs occur that necessitate lowering the dose of irinotecan. A Rickham reservoir/catheter system will be placed at the time of surgery for delivering repeat doses of NSCs intracranially. MRIs and PET/CT scans of the brain will be performed at least every two months (at the end of every even cycle of study treatment to evaluate response).

Three doses of NSCs will be assessed. The starting dose will be  $5 \times 10^7$  NSCs, which was well-tolerated in the first-in-human study of CD-expressing NSCs. Due to volume limitations for intracerebral administration, the highest dose of NSCs to be tested will be  $1.5 \times 10^8$  cells. Study participants will receive repeat cycles of study treatment (dose level 1 and -1 patients will only receive repeat doses of irinotecan) as long as they are tolerating the treatment well, and there is no evidence of progressive disease.

An important secondary objective of this study will be to determine the biologic activity of the hCE1m6-NSCs by measuring concentrations of SN-38 in brain interstitium using intracerebral microdialysis. The first 6 patients to enroll in the study and the last 8 patients in the expansion cohort will undergo microdialysis to collect data regarding intracerebral levels of irinotecan and SN-38 when patients are treated with the lowest and highest NSC doses. Please note, the same dose of NSCs ( $5 \times 10^7$ ) is given to patients on dose levels 1 and 2, so whether the first 6 patients are all treated on dose level 1 or the first 3 dose level 1 and the next 3 on dose level 2, they will all receive the same dose of NSCs.

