## Assigning Treatment and Correlative Study Regimen

---

A participant's starting NSC dose level, irinotecan dose schedule, correlative study procedures, and NSC regimen will be assigned by the Principal Investigator based on the following criteria:

1. Except where planned in the expansion cohort, participants who do not receive Day 1 NSCs will be replaced.
2. During the 3+3 stage of the trial, any participants who are not evaluable for dose escalation will be replaced.
3. During the 3+3 stage of the trial, the NSC dose level (-1,1,2,3, or 4) and irinotecan dose schedule (A, B, or C) will be determined using criteria defined in Section 5.3.
4. The first six patients enrolled to the trial will have microdialysis catheters inserted and undergo microdialysis and accompanying blood plasma PK studies. If one or more of the six patients does not receive cycle 1 day 3 irinotecan, the patient(s) will be replaced with the next patient(s) enrolled.
5. During the expansion cohort, all eight participants will have microdialysis catheters inserted and undergo microdialysis and accompanying blood plasma PK studies. N.B., since it is anticipated that the MTD/MFD will be 150 million NSCs (dose level 4), the 6 patients who will be treated on dose level 4 will undergo intracerebral microdialysis and be counted as part of the expansion cohort.
6. During the expansion cohort, all 8 participants will follow the NSC dose level and irinotecan dose schedule per the MTD (or if the MTD is not reached, the MFD), however 4 participants will receive their initial NSC administration on the day of surgery (Day 1), and 4 participants will receive their first NSC administration on Day 15. Participants will be grouped according to surgery type (craniotomy or biopsy). As each group enrolls participants, it will alternate between enrolling the participant to the Day 1 NSC start date and the Day 15 NSC start date. (See Section 5.4 for further explanation).

Based on the above criteria, the Principal Investigator will communicate to the clinical research team and the neurosurgeon the assigned biopsy or craniotomy procedure A-K as detailed in table 8.2a and table 8.2b.

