#### **Treatment Plan: Expansion Cohort**

---

After the MTD/MFD of the combination therapy is defined, an expansion cohort of 8 patients will be treated to gain more experience regarding the tolerability of study treatment at the MTD/MFD and to assess the biological activity of the hCE1m6-NSCs using intracerebral microdialysis. Since it is anticipated that the MTD/MFD will be 150 million NSCs (dose level 4), the 6 patients who will be treated on dose level 4 will undergo intracerebral microdialysis and be counted as part of the expansion cohort.

Four patients in the expansion cohort will undergo intracerebral microdialysis after receiving NSCs at the time of surgery followed 2 days later by IV irinotecan, but the other 4 patients in this cohort will not receive NSCs on the day of surgery. Instead they will be given IV irinotecan 2 days after surgery, and dialysate samples will be collected from them to determine how much SN-38 is present in the brain from treatment with IV irinotecan alone. These 4 patients will then receive their first dose of NSCs through the Rickham on day 15 of cycle 1 followed by irinotecan on day 17.

To determine who will receive their initial NSCs administration on the day of surgery, and who will receive their first NSC administration on Day 15 via the Rickham catheter, participants will be stratified according to surgery type (craniotomy or biopsy), and, as each group enrolls participants, it will alternate between enrolling the participant to the Day 1 NSC start date and the Day 15 NSC start date. For example, the first craniotomy participant will be assigned Day 1 NSC start date, the second craniotomy participant will be assigned Day 15 NSC start date, the third will be assigned Day 1 NSC start date, the fourth will be assigned Day 15 NSC start date, and so on as applicable. The same alternate enrollment scheme will apply to participants undergoing the biopsy procedure. The rationale for this plan is to ensure to the degree possible an even distribution of start dates for each surgery group which should increase the ability for direct comparison. There is no requirement for specific number of biopsy or craniotomy participants in the expansion cohort.

If the DLT rate in the expansion cohort exceeds 34%, the toxicity data will be reviewed.

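### Section 15.1 takes its DLT precision from 14 patients at the MTD/MFD, but counting the six level-4 patients inside the eight-patient expansion cohort, as five places do, gives only 8 on the anticipated path

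*Combined protocol and SAP*

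**What the plan says.** Section 15.1 (Sample Size) first gives figures for 6 patients at the MTD/MFD: a maximum 95% margin of 0.38 for the DLT rate, and detection of a 0.25 toxicity rate in about 82% of trials. It then adds the expansion cohort, "The additional 8 patients in the expansion cohort, for a total of 14 patients treated at the MTD/MFD", and states a margin of 0.27 and detection of a 0.15 rate in about 90% of trials.

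Section 5.4 sets the expansion cohort at 8 patients. It also anticipates that the MTD/MFD will be dose level 4 and says that "the 6 patients who will be treated on dose level 4 will undergo intracerebral microdialysis and be counted as part of the expansion cohort". The same sentence stands in Section 5.2, item 5, and in footnote d of the dose escalation schema in the Experimental Design Schema, the Synopsis and Section 5.

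Other wording points to, or at least fits, a separate cohort:

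- Section 5.4: "After the MTD/MFD of the combination therapy is defined, an expansion cohort of 8 patients will be treated"
- Synopsis (Study Design) and Section 2.9: "the last 8 patients in the expansion cohort will undergo microdialysis"
- Section 15.1, within the build-up of the maximum sample size: "an additional 8 patients for the expansion cohort"

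**The concern.** If six of the eight expansion patients are the six already treated at level 4, they cannot also be added to the eight. The total at the MTD/MFD is then 8, and the figures for 14 describe a data set that the enrolment rules would not produce. This happens on the path the protocol itself expects.

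The primary objective is the recommended phase II dose, based on the MTD/MFD and its toxicity profile. The DLT precision at that dose is therefore the planning statement for the primary endpoint. A reader of Section 15.1 would think the trial has about a 10% chance of seeing no case of a toxicity with a true rate of 0.15. Under the overlap that chance is about 27%.

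**Working it through.** **Inputs.** From Section 15.1: n=6 with margin 0.38 and 82% detection at a rate of 0.25; n=14 with margin 0.27 and 90% detection at 0.15. From Section 5.4: expansion cohort of 8, with the six level-4 patients counted in it. From the Analysis Plan in Section 15.3: 95% Clopper-Pearson limits.

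**Formulas.** The margin is the largest half-width of the exact 95% Clopper-Pearson interval over all possible numbers of DLTs. Detection is the probability of at least one event, 1 − (1 − p)^n.

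**Step 1: reproduce the plan's figures.**

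| n | Maximum half-width | Detection |
|---|---|---|
| 6 | 0.382 (stated 0.38) | 1 − 0.75^6 = 0.822 (stated 82%) |
| 14 | 0.270 (stated 0.27) | 1 − 0.85^14 = 0.897 (stated 90%) |

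All four figures reproduce. Neither the Wald margin (0.400 and 0.262) nor the Wilson half-width (0.312 and 0.232) matches the stated pair. The method is therefore clear, and only n is in question.

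**Step 2: count the patients.**

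- Separate cohorts: 6 + 8 = 14.
- Overlap with level 4 as the MTD/MFD: 8 − 6 = 2 added, so 6 + 2 = 8.
- MTD below level 4: the overlap sentence, which concerns level 4 only, does not apply, and 14 can stand.

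**Step 3: apply the same formulas to n=8.**

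| Quantity | n=14 | n=8 |
|---|---|---|
| Maximum 95% half-width | 0.270 | 0.343 |
| Detection of a 0.15 rate | 0.897 | 1 − 0.85^8 = 0.728 |
| Rate detected with 90% probability, 1 − 0.10^(1/n) | 0.152 | 0.250 |
| 95% limits with 0 DLTs | 0 to 0.232 | 0 to 0.369 |
| 95% limits with 1 DLT | 0.002 to 0.339 | 0.003 to 0.527 |

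The chance of seeing no event when the true rate is 0.15 is 1 − 0.897 = 0.103 with 14 patients and 1 − 0.728 = 0.272 with 8.

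**Step 4: does the anticipated total of 29 settle it?** No. The documents do not show how 29 is built, and both readings can reach it. As illustrations, 18 + 3 + 8 = 29 with a separate cohort, and 24 + 3 + 2 = 29 with the overlap.

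**The case against.** The strongest reply is that little depends on these figures. The plan tests no hypothesis about the DLT rate, the 3+3 rules do not use Section 15.1, and the final limits will be calculated on whatever n is observed. That is correct, and it confines the point to planning precision. It does not make the two counts agree.

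A second reply is that 8 is not the only possible total under the overlap. If all six level-4 escalation patients start NSCs on Day 1 and four Day-15 starters are still required, the total is 6 + 4 = 10, with a half-width of 0.313 and 80.3% detection of a 0.15 rate. This would need an expansion cohort larger than the stated 8. The alternating assignment in Section 5.4 can reach 4:4 within 8 if it is applied to the escalation patients at level 4 as well. Even 10 patients would not deliver the stated figures.

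A third reply is that some of the separate-cohort wording does not discriminate. The phrase about the last 8 patients also fits the overlap, since six level-4 patients plus two more would be the last eight enrolled. The additional 8 in the build-up of the maximum may describe a case in which the MTD lies below level 4. Both observations stand. Clearer support for a separate cohort comes from the opening of Section 5.4 and from the total of 14 itself. Table 8.2b also lists a level-4 procedure without microdialysis (J), which would be largely unused if every level-4 patient had microdialysis. This evidence bears on which reading the sponsor intended; it does not remove the conflict.

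**Conclusion.** The inconsistency is real and should be corrected. If the overlap applies and level 4 is the MTD/MFD, as the protocol anticipates, Section 15.1 overstates its planning precision: the margin is 0.34 instead of 0.27, and detection of a 0.15 rate is 73% instead of 90%.

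This conclusion rests on the expansion cohort staying at 8 and on the overlap sentence meaning what it says. If the overlap is not intended, or the MTD is a lower level, 14 can stand. The documents do not say which reading is meant. Dose-escalation decisions and the final Clopper-Pearson limits are unaffected, and the power of the exploratory SN-38 comparison is not part of this point.

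**What to change.** Reconcile Section 15.1 with the expansion-cohort text in one of two ways.

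1. **Keep the overlap.** State in Section 15.1 that, when level 4 is the MTD/MFD, 8 patients are treated there, giving a maximum margin of 0.34 and 73% detection of a 0.15 rate (or 90% of a 0.25 rate). Keep the 14-patient figures for a lower MTD. The cost is wording and less favourable figures; restating them adds no patients.
2. **Drop the overlap.** Remove the sentence from all five places so that 14 stands. The cost is 14 − 8 = 6 more patients at level 4 than under the overlap. The same sentence assigns microdialysis to the six level-4 escalation patients, so the sponsor should say whether that still applies.

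Under either option, show how the anticipated total of 29 is made up.

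If the overlap is kept, one clarification is needed: whether a planned Day-15 starter counts for dose escalation under the 80% rule in Section 5.3. The rule refers to the treatment for a dose level, which can be read as two cycle-1 NSC doses. Section 5.2 points the other way: it says that the "NSC regimen will be assigned by the Principal Investigator based on the following criteria", and its item 1 reads "Except where planned in the expansion cohort, participants who do not receive Day 1 NSCs will be replaced". Item 6 provides that "4 participants will receive their first NSC administration on Day 15". If those four do not count, a 4:4 split leaves only 8 − 4 = 4 countable patients. Six could then not be reached within 8 unless Day-15 starters have a DLT or are replaced.

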### Accrual Rate

---

Given that the first 3 patients entering a cohort until the MTD/MFD is determined will enter sequentially after the prior patient completes cycle 1, the study time is mostly determined by cycle length. It is anticipated that this study will complete accrual within approximately 36 months.

### Statistical Design and Analysis

---

#### 15.1.1 Design:

---

The dose escalation plan is based on a standard 3+3 design and is described in section 5.3.

#### 15.1.2 Primary Objectives

---

To define the recommended phase II dose (RP2D) of intracranially administered hCE1m6-NSCs in combination with intravenous irinotecan in patients with recurrent high grade glioma. The RP2D will be based on the maximum-tolerated dose (MTD), or if the MTD is not reached, the maximum feasible dose (MFD), and the full toxicity profile including toxicities associated with repeat doses of NSCs.

#### 15.1.3 Secondary Objectives

---

- To describe the relationship between hCE1m6-NSC dose and SN-38 concentrations in brain interstitium.
- To characterize the relationship between intracerebral and systemic concentrations of irinotecan and SN-38.
- To investigate the biologic activity of hCE1m6 NSCs by comparing SN-38 concentrations in the brain after treatment with hCE1m6-NSCs and irinotecan versus irinotecan alone.
- To assess for possible development of adenovirally transduced NSC immunogenicity after first exposure and with repeat doses of NSCs.

- To describe the clinical benefit (defined as stable disease, partial response, or complete response) in patients who receive treatment with repeat cycles of NSCs and irinotecan.
- To determine, at time of autopsy, the fate of the NSCs.

#### 15.1.4 Primary Endpoints:

---

- Safety and Feasibility:
  - For Dose Escalation: Dose Limiting Toxicities
  - Toxicity Profile: All Attributable Toxicities

#### 15.1.5 Secondary Endpoints:

---

- Pharmacokinetics:Cmax and AUC of irinotecan and SN-38 in dialysate and plasma.
- Immunogenicity:Evaluate patient blood samples for the development of T cell responses and antibodies against the NSCs using TcR V $\beta$  spectratyping, CD 107 degranulation assays, and flow cytometry. Measure patients' serial adenoviral antibody titers.
- Clinical benefit: Tumor response based on brain MRI and PET/CT scans results
- Determine the Fate of the NSCs: NSC persistence

#### 15.1.6 Analysis Plan:

---

Tables will be created to summarize all toxicities and side effects by dose, course, organ severity (by NCI CTCAE version 4.0), and attribution. Rates and associated 95% Clopper Pearson confidence limits will be estimated for DLTs and clinical benefit at the RP2D. Descriptive statistics will be provided for study patient demographics.

Pharmacokinetic data from patients who undergo intracerebral microdialysis will be summarized using descriptive statistics and graphical methods. The biologic activity of the hCE1m6-NSCs, based on comparison of microdialysis SN38 PK data from patients receiving NSCs + irinotecan vs patients receiving irinotecan alone, will be assessed using a one-sided two-sample t test. Regression analysis will be used to assess the relationship between hCE1m6-NSC dose and SN-38 concentrations in brain interstitium using microdialysis data from the patients treated with the initial NSC dose (n=6) and from the patients in the expansion cohort treated with the highest NSC dose (n=4). Other secondary objectives include assessing for possible development of NSC immunogenicity after first and repeat exposures, and—when feasible—evaluating the fate of the NSCs at autopsy. These results will be summarized using descriptive statistics and graphical methods.

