#### 5.1.4 Definition of Maximum Tolerated Dose and Maximum Feasible Dose

---

The MTD/MFD will be based on the assessment of DLTs as defined in Section 5.3.3. The MTD is the dose level at which 0/6 or 1/6 participants experience a DLT with the next higher dose having at least 2/3 or 2/6 participants encountering a DLT. If the MTD has not been reached with NSC dose level 4 and irinotecan schedule A, then that dose level will be termed the maximum feasible dose (MFD).

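### The DLT rate planned at the RP2D includes six patients who had to show at most 1/6 DLTs for that dose to be chosen, so the pooled point estimate is biased low

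*Combined protocol and SAP*

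**What the plan says.** The Analysis Plan (15.1.6) states "Rates and associated 95% Clopper Pearson confidence limits will be estimated for DLTs and clinical benefit at the RP2D". It gives no analysis set for that rate and no remark on how the dose was chosen.

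The only denominators are in Section 15, Sample Size. Six patients at the MTD/MFD are said to "achieve a maximum margin of error for a 95% confidence interval for the DLT rate of 0.38" and to "detect a 0.25 toxicity rate in approximately 82% of trials". Then: "The additional 8 patients in the expansion cohort, for a total of 14 patients treated at the MTD/MFD", which is said to "achieve a maximum margin of error for a 95% confidence interval for the DLT rate of 0.27" and to "detect a 0.15toxicity rate in approximately 90% of trials".

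The selection rule is in 5.1.4: "The MTD is the dose level at which 0/6 or 1/6 participants experience a DLT". Section 5.1.2 treats two or more DLTs in three or six patients as exceeding the MTD, so the same ceiling applies if dose level 4 becomes the MFD.

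Two other places matter. Section 5, under Assigning Treatment and under Treatment Plan: Expansion Cohort, counts the six dose level 4 patients within the expansion cohort of eight if that level is the MTD/MFD. The same sections give four of the eight expansion patients no NSCs on Day 1; these patients start on Day 15.

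**The concern.** A Clopper-Pearson interval and a simple proportion assume that the count was free to take any value. For the six escalation patients it was not: a dose with 2/6 or more would not be the MTD/MFD. Their observed rate is therefore low partly by construction, and pooling carries that into the reported figure.

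Defining the RP2D is the primary objective and DLTs are a primary endpoint. This rate will inform the risk expected in phase II for an intracranial cell product. The bias has a known direction, and the plan neither separates the selected patients nor mentions the effect.

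**Working it through.** **1. The plan's own figures reproduce.** The maximum Clopper-Pearson half-widths are:
- n=6, at 3/6: (0.118, 0.882), half-width 0.382, stated as 0.38.
- n=14, at 7/14: (0.230, 0.770), half-width 0.270, stated as 0.27.

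The detection figures are chances of at least one event: 1 − 0.75^6 = 0.822 (stated as 82%) and 1 − 0.85^14 = 0.897 (stated as 90%).

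**2. What the six can show at the selected dose.** Under 5.1.2 and 5.1.4 only two results are possible:
- 0/6: (0, 0.459), half-width 0.230.
- 1/6: (0.004, 0.641), half-width 0.318.

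**3. Expected count given selection.** Let X be the DLT count in the six and p the true rate. Then

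E[X | X ≤ 1] = 6p(1−p)^5 / [(1−p)^6 + 6p(1−p)^5] = 6p / (1 + 5p).

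At p = 0.30 this is 1.8/2.5 = 0.72 DLTs, against 1.8 without selection.

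**4. Expected pooled rate.** The m patients enrolled after the decision are taken as unselected, because their count does not choose the dose. A DLT rate above 34% in the expansion cohort triggers only a review. The expected rate is [6p/(1+5p) + mp] / (6 + m). At p = 0.30:
- m = 8: (0.72 + 2.4)/14 = 0.223.
- m = 2: (0.72 + 0.6)/8 = 0.165.

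The documents give no true rate, so a range is assumed:

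| Assumed true rate | Six only | 6+8 pooled (bias) | 6+2 pooled (bias) |
|---|---|---|---|
| 0.10 | 0.067 | 0.086 (−0.014) | 0.075 (−0.025) |
| 0.20 | 0.100 | 0.157 (−0.043) | 0.125 (−0.075) |
| 0.25 | 0.111 | 0.190 (−0.060) | 0.146 (−0.104) |
| 0.30 | 0.120 | 0.223 (−0.077) | 0.165 (−0.135) |
| 0.33 | 0.125 | 0.242 (−0.088) | 0.176 (−0.154) |

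**5. Check by simulation.** The NSC escalation rules were simulated 40,000 times for each of three assumed dose-toxicity curves. The selected dose never had more than one DLT among its six.

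| Mean true rate at selected dose | Six | Pooled 14 | Eight later patients only |
|---|---|---|---|
| 0.171 | 0.089 | 0.136 | 0.171 |
| 0.202 | 0.097 | 0.156 | 0.201 |
| 0.125 | 0.075 | 0.104 | 0.126 |

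**6. Interval coverage given selection (exact enumeration).** For the pooled 14, the upper limit falls below the truth in:
- 0% of selected trials at true rates of 0.10 and 0.20,
- 3.3% at 0.25, 1.6% at 0.30 and 1.0% at 0.33,
- 6.4% at 0.35 (about 2% for an unselected 14) and 3.5% at 0.40.

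The lowest total coverage among the rates tried up to 0.33 is 96.6%, at 0.25. At 0.35 it is 93.6%. With 6+2 patients the upper limit never misses at the rates tried up to 0.35; at 0.40 total coverage is 92.8%. A dose passes the six-patient screen with probability 32% at a true rate of 0.35 and 23% at 0.40.

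**The case against.** The strongest reply is that this is one descriptive summary and not the decision rule. The RP2D also rests on the full toxicity profile, toxicities are tabulated by dose, course and attribution, and the expansion cohort has its own review trigger. The Analysis Plan does not itself say that the six are pooled; that comes from Sample Size. All of this stands and limits the consequence. It does not remove the bias, since 14 is the only total the plan gives for the DLT rate at the MTD/MFD.

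A reader might infer four stronger points that the documents do not support.

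- **That 0.38 is an error.** It is labelled a maximum and is the correct worst case for n=6. The dose rule makes 3/6 unreachable at the MTD/MFD, so the figure is conservative as a half-width.
- **That 82% should be 67%.** Given selection, the chance of at least one DLT in the six at p = 0.25 is 6p/(1+5p) = 1.5/2.25 = 67%. But the plan speaks of a toxicity rate, and selection acts on DLTs. For a toxicity that is independent of DLTs, 82% stands.
- **That the upper confidence limit is generally too reassuring.** The 6.4% at 0.35 is the worst rate checked for the pooled 14, and such a dose seldom passes the screen.
- **That patients enrolled after the decision should supply the main estimate.** Four of the eight expansion patients receive no Day 1 NSCs, yet DLTs are counted in cycle 1. Their rate is therefore not plainly that of the full regimen. If the six level 4 patients count in the eight, only two new patients remain: 0/2 gives 0 to 0.84 and 1/2 gives 0.01 to 0.99.

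**Conclusion.** The concern holds as a reporting defect in a primary endpoint. On the 14-patient denominator the point estimate is biased low by about 0.01 at a true rate of 0.10, 0.04 at 0.20 and 0.08 at 0.30. If only two patients follow the six, the shortfall is about 0.03, 0.08 and 0.14. That second count is the one Section 5 anticipates, since it expects dose level 4 to be the MTD/MFD. Interval coverage is mostly kept up to a true rate of about 0.33.

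This rests on four assumptions: the rate is computed on the pooled patients, as Sample Size implies; the RP2D is the MTD/MFD; the true rate lies in the range shown; and later patients share the same DLT rate as the six. The last is uncertain for those who start NSCs on Day 15.

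**What to change.** **Analysis Plan.** Report the DLT count, rate and Clopper-Pearson limits separately for (a) the six escalation patients at the MTD/MFD and (b) patients enrolled after the MTD/MFD decision, with (b) split by Day 1 and Day 15 NSC start. Show the pooled rate beside them, labelled as including six patients selected on at most 1/6 DLTs.

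**Sample Size.** Keep 0.38 as a worst-case bound. Add that at the MTD/MFD the six can give only 0/6 (0 to 0.46) or 1/6 (0.004 to 0.64).

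**Counts.** Reconcile the total of 14 in Sample Size with the counting of the six within the cohort of eight in Section 5. Quote 0.34 as the maximum half-width for post-decision patients (4/8: 0.157 to 0.843, half-width 0.343) only if eight new patients are enrolled. If only two are, say so.

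**Cost.** Wording changes and one or two extra table rows with wide intervals. No dose rule, sample size or procedure has to change for the separate reporting.
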